1.1. Study summary

Design

Patients will be randomized to receive either 30mg of atorvastatin or be presented with a choice of receiving either a “natural” statin (red yeast rice extract) or 30mg of atorvastatin.

In the intervention arm, a goal of either LDL-C reduction of at least 50% or an LDL-C < 100 mg/dl will be discussed on the initial visit. Goals will be re-assessed at 2 months, if goals are not met, patients will be given 30mg of atorvastatin.

Aims

To assess if introducing greater patient autonomy increases patient compliance with statin therapy.

Outcome measures

The primary endpoint will be 6-month compliance of statin therapy, after the initiation of atorvastatin.

Secondary endpoints will be rates of perceived side effects from statin use, including myalgias, fatigue, mental fog and GI upset.

Population

This will be a multi-center study of 300 pts, 150 in each arm.

Eligibility

Primary prevention (no history of CAD, MI, or stroke) patients with a moderate 10-year ASCVD risk who decline statin therapy.

Duration

Anticipated recruitment is 6 months. Follow-up will be performed at 6 months in the control arm and 2 and 8 months in the intervention arm, for a total study duration of 14 months.

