1.1. Study overview diagram

4.2 Study protocol:

Patients meeting the study criteria will be enrolled at outpatient cardiology clinics at four centers: Lithuanian University of Health Sciences, Northway Medical Centre, Prienu Hospital, and Unomeda Medical Centre. The enrolment period will last six months, with an estimated 50 patients per month enrolled into the study, for a total of 300 patients.

Patients will be randomized to either the control group or the intervention group. Baseline variables will include demographic variables (age, gender, BMI, blood pressure, heart rate), medical history (hypertension, hyperlipidaemia, type 2 diabetes mellitus, tobacco use), laboratory variables (total cholesterol, HDL, LDL, triglycerides, AST, ALT, creatine kinase, and, vitamin D levels) and socioeconomic variables (education level, income level, rural or urban, and marriage status).

The control group will be provided reassurance through a short, semi-structured discussion on the excellent safety profile of statins, similar to a typical interaction between a clinician and patient. They will then be prescribed 30mg atorvastatin daily as a 30 tablets supply with five patient-initiated re-fills for 30 tablets each. Final follow-up in this group will occur at 6 months.

The intervention group will be offered a red yeast rice extract 20mg nightly to achieve a goal LDL-cholesterol of <2.6 mmol/L (100 mg/dL) in accordance with the 2019 ESC/EAS guidelines (9). Initial follow-up will take place in 2 months to assess the efficacy of their treatment. Patients who are not at the goal LDL-cholesterol will be prescribed 30mg atorvastatin nightly as a 30 tablets supply with five patient-initiated re-fills for 30 tablets each, with final follow-up after 6 additional months. Patients who are at goal on the red yeast rice extract will be recommended to switch to lovastatin 20mg nightly as a bio-identical substitute, but they will be excluded from further analysis.

In both groups, statin adherence will be assessed by pharmacy refill records at the final follow-up. A short, four question questionnaire (Appendix A) will be administered at this point as well. Final follow-up laboratory variables collected will include total cholesterol, HDL, LDL, triglycerides, AST, ALT, creatine kinase, and vitamin D levels.

Conversation guidelines for each clinical encounter in the intervention group are included in Appendix B.

Randomisation

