4.3. Study outcome measures

Primary Endpoint

Rate of statin compliance, based on pharmacy refill records. Values per patient can range from 0-6 according to the number of refills.

Secondary Endpoints:

Rate of perceived side-effects from statin use, including muscle aches, fatigue, mental fog, and gastrointestinal upset.

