6.2 Reporting procedures

Clinical Events Committee

The CEC is made up of cardiologists who are not participants in the trial. The CEC is charged with the development of specific criteria used for the adjudication of clinical events and clinical endpoints in the trial which are based on protocol.

The Clinical Events Committee will establish explicit rules outlining the minimum amount of data required, and the algorithm followed in order to classify a clinical event. All members of the Clinical Events Committee will be blinded to the treatment arm and the primary results of the trial.

The Clinical Events Committee will meet regularly to review and adjudicate all clinical events in which the required minimum data is available. The Committee will also review and rule on all deaths that occur throughout the trial.

Reports of clinical events should be submitted within 15 days of the Chief Investigator becoming aware of the event.

Local investigators should report any clinical events as required by their Local Research Ethics Committee, Sponsor and/or Research & Development Office.

Contact for reporting clinical events: [name]
Email: [contact]

Case report form

An online CRF form will be used throughout the study. This will be secure, and compatible with currently guidelines to ensure security of patient data. It will be managed via the Lithuanian University of Health Sciences Clinical Trials Unit , and data achieved securely.

7. Assessment and follow-up

Routine follow-up will be performed with a clinic visit at 6 months in the control group and at 2 months and 8 months in the intervention group. The CRF should be completed.

8. Statistics and data analysis

Data will be summarised as mean (SD) or median (interquartile range) for skewed data. Statistical comparisons will be undertaken using a paired Student's t-test (after log transformation if necessary) or nonparametric alternative if data are not normalised by log transformation. Kaplan-Meier survival analysis curves will be used to assess clinical event timelines.

9. Regulatory issues

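### The primary refill count runs to the final visit, not to a fixed day after the atorvastatin prescription, so off-schedule visits or a statin start at entry can give the two arms different counting windows

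*Protocol*

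**What the plan says.** The study summary (Protocol section 1.1) gives both the length and the anchor of the endpoint: "The primary endpoint will be 6-month compliance of statin therapy, after the initiation of atorvastatin".

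The rules that would produce the number are in two other places. Section 4.2 sets when it is read: "In both groups, statin adherence will be assessed by pharmacy refill records at the final follow-up". Section 4.3 sets the score: "Values per patient can range from 0-6 according to the number of refills". Neither names a start date, a last countable day or the use of dispensing dates.

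The visit schedule is as follows.

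- Control: atorvastatin is prescribed at entry. "Final follow-up in this group will occur at 6 months" (section 4.2).
- Intervention, not at LDL goal at two months: atorvastatin is prescribed at that visit, "with final follow-up after 6 additional months" (section 4.2).
- Section 7 counts from entry instead: "at 6 months in the control group and at 2 months and 8 months in the intervention group". The summary gives the same months.

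Supply is the same in both arms, a "30 tablets supply with five patient-initiated re-fills for 30 tablets each", so the maximum is 1 + 5 = 6 fills, or 180 tablets.

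The summary also says that intervention patients choose between red yeast rice and atorvastatin. Section 4.2 gives no follow-up schedule for those who choose atorvastatin at entry.

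**The concern.** A count of fills grows with the time over which it is taken, until it reaches the cap of six. If the window ends at a visit, its length depends on when that visit takes place. In the control arm, prescription and clock both start at entry. In the intervention arm the prescription normally comes at a second visit, which can be early or late, and the final visit is timed from entry in one place and from the prescription in another. That arm therefore has a source of window variation that the control arm lacks.

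The target difference is small, a fraction of one fill. A systematic difference in window length would be read as a difference in compliance. A shorter intervention window would hide a true effect, and a longer one could create a false effect.

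**Working it through.** **The plan's own figure.** Section 4.5 assumes 50% compliance, SD 10%, a 5-point effect, alpha 0.05, power 0.9 and 1:1 allocation, and gives a total of 138. With n per arm = 2(z_alpha + z_beta)² × (SD/difference)²:

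- One-sided: 2 × (1.645 + 1.282)² × (10/5)² = 68.5, so 69 per arm and 138 in total. This matches.
- Two-sided: 85 per arm, 170 in total. This does not match.

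Section 4.5 does not state the sidedness. That is a separate matter; the one-sided version is used below because it reproduces the plan.

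**The target in fills.** 5% of 6 = 0.30 fill per patient. One fill is 100/6 = 16.7 points.

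**Nominal windows.** Control: month 0 to month 6 = 6 months. Intervention: month 2 to month 8 = 6 months. They agree.

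**Where they part.**

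- (a) The two-month visit takes place at month 3 and the final visit stays at month 8: 8 − 3 = 5 months. An early two-month visit lengthens the window instead.
- (b) An intervention patient starts atorvastatin at entry and is read at month 8: 8 months against 6 in control, about 61 days more.

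**Size if refilling is steady (assumption).** 50% of 6 fills is 3 fills in 180 days. A change of d days then shifts the score by d × (3/180)/6 × 100 points.

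| Change in window | Points |
|---|---|
| 7 days | 1.9 |
| 14 days | 3.9 |
| 18 days | 5.0 |
| 28 days | 7.8 |
| 30 days | 8.3 |
| 61 days | 16.9 |

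In case (b), 5/16.9 = 30% of the analysed intervention patients would have to start at entry to shift the arm mean by the full 5 points. The documents do not give that share.

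**Size under two simulated refill patterns (assumptions).** The first fill falls in the first 7 days, the base window is 182 days and the cap is six fills.

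| Pattern | Base score | −28 days | +28 days | +61 days |
|---|---|---|---|---|
| Stretched gaps, mean 50 days | 68.5% | −9.4 | +9.3 | +19.6 |
| Stretched gaps, mean 60 days | 58.6% | −7.7 | +7.8 | +16.9 |
| Stretched gaps, mean 75 days | 48.8% | −6.4 | +6.1 | +13.5 |
| Early stopping, 70% continue at each fill | 48.0% | −2.4 | +1.1 | +1.0 |
| Early stopping, 75% continue | 53.5% | −3.3 | +1.3 | +1.3 |
| Early stopping, 80% continue | 59.7% | −4.6 | +1.6 | +1.8 |

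The 75-day row is the stretched pattern nearest the plan's 50%. There, +21 days gives 4.6 points and +28 gives 6.1, so 5 points needs about 21 + 7 × (0.4/1.5) = 23 days, a little more than the 18 from simple proportion.

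**Effect on the test** (69 per arm, one-sided 0.05, SD 10). A spurious shift of 2.3 points, which is 18 × 2.3/5 = about 8 days under steady refilling, raises the rejection rate with no true effect from 5% to 38%. The same shift against a true 5-point effect cuts power from 90% to 48%.

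**The boundary day.** A patient filling every 36 days fills on days 0, 36, 72, 108, 144 and 180. The score is 6 if day 180 counts and 5 if it does not. A patient filling every 45 days (0, 45, 90, 135, 180) scores 5 or 4 by the same rule. One fill is 16.7 points for that patient, so the rule has to be stated once.

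**The case against.** The strongest reply is that a window exists. The summary gives six months from the start of atorvastatin, which is almost the rule proposed here, and pharmacy records would normally carry dates. That stands as to intent. It does not settle the operative rule, because section 4.2 reads the records at the visit and section 4.3 counts fills without a cut-off.

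A reader might infer that month 8 and six further months contradict each other, or that the arms have different windows by design. The documents do not support either: 2 + 6 = 8, and both arms have six months when visits are on time. The windows part only in cases (a) and (b). Case (a) also requires that staff hold the final visit at month 8 and do not follow section 4.2.

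A reader might also infer that variable visit dates bias the result in themselves. They do not. Variation that is equal in both arms adds noise; bias needs a systematic difference between the arms. The documents report no slippage, and the six-fill cap limits the gain from late readings when patients stop early.

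Visit tolerances and the exact cut-off may be in a statistical analysis plan that is not shown, and their absence here is not the point. The point is that the protocol itself ties the count to the visit. Access to the records of patients who miss that visit must also be settled in consent, which a later analysis plan cannot do.

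Finally, a reader might infer that the count is invalid and must give way to days covered. Fills on days 0, 170, 175 and 178 do score 4 of 6 (67%) with only 30 + 10 = 40 of 180 days covered (22%). But the pattern is contrived, nothing suggests that it would differ by arm, and the 0 to 6 count is a defined measure with the same cap in both arms.

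**Conclusion.** The point holds in a limited form. The rule in sections 4.2 and 4.3 does not secure the endpoint that the summary defines, and the arms are exposed unequally when the two-month visit is off schedule or atorvastatin starts at entry.

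The size depends on assumptions. With steady refilling at 50%, a systematic between-arm difference of about 18 days (about 23 in the nearest simulation) equals the whole target. With early stopping, 28 extra days add under 2 points, while 28 fewer cost 2.4 to 4.6, from about half to most of the target. Whether any such difference will arise cannot be told from the documents. The change is worth making because it removes the dependence on visit timing at little cost, not because a bias has been shown.

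**What to change.** - In sections 4.2 and 4.3, define the primary score as the number of fills with a dispensing date within 180 days of that patient's atorvastatin prescription, whatever the date of the final visit. State one boundary rule, for example days 0 to 179 with the prescription date as day 0.
- Extract the records for every patient prescribed atorvastatin, whether or not the final visit is attended. Patients at LDL goal who are moved to lovastatin have no atorvastatin date, so this window cannot be applied to them; their exclusion under section 4.2 is a separate question.
- State that the window also runs from the prescription for intervention patients who start atorvastatin at entry.
- Reconcile month 8 from entry (sections 1.1 and 7) with six additional months (section 4.2) for the case where the two-month visit is off schedule.
- Proportion of days covered, from the same dates, can be a supportive analysis.

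The cost is endpoint wording and extraction of dispensing dates. It adds no patients or visits and leaves the calculation behind 138 unchanged, because the 0 to 6 score is kept. The small downside is that consent must cover record access for patients who miss the final visit.

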Patients will be randomized by block randomization. On the first week of enrollment, the clinician will only enroll patients into the control arm. On the subsequent week, the clinician will only enroll patients into the intervention arm.

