6.1. Definitions

The following definitions will be employed in this study.

Statin intolerance

Development of an increase in creatine kinase OR AST/ALT elevation > 3x upper limit of normal OR rhabdomyolysis with statin initiation during the study period.

History of statin intolerance

History of an increase in creatine kinase OR AST/ALT elevation > 3x upper limit of normal OR rhabdomyolysis with statin initiation, prior to enrollment in this study

Moderate risk for ASCVD

7.5%-20% 10-year ASCVD risk by the Pooled Cohorts Equation

Severe Mental Illness

History of schizophrenia or another mental illness with psychotic features

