Appendix A Final Follow-up questionnaire

Have you had any of the following symptoms from atorvastatin over the past 6 months?			
Myalgias (muscle aches)	 Yes	 No	 Not Sure
Fatigue	 Yes	 No	 Not Sure
Mental fog (slow thinking or memory issues)	 Yes	 No	 Not Sure
Gastrointestinal upset	 Yes	 No	 Not Sure

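### The four side-effect symptoms have no enrolment counterpart and prior statin use is not recorded, so precision is lost and a symptom imbalance between the analysed groups could be neither seen nor adjusted for

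*Protocol*

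**What the plan says.** Section 4.3 of the protocol names one secondary endpoint: "Rate of perceived side-effects from statin use, including muscle aches, fatigue, mental fog, and gastrointestinal upset". The same outcome appears in the primary objective and the hypothesis (section 3).

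It is measured by Appendix A, which asks "Have you had any of the following symptoms from atorvastatin over the past 6 months", with the answers Yes, No or Not Sure. Section 4.2 places it at the final visit only: "A short, four question questionnaire (Appendix A) will be administered at this point as well". That visit is at 6 months in the control arm and 8 months in the intervention arm.

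Section 4.2 itemises the baseline variables: demographic and socioeconomic items, "medical history (hypertension, hyperlipidaemia, type 2 diabetes mellitus, tobacco use"), and "laboratory variables (total cholesterol, HDL, LDL, triglycerides, AST, ALT, creatine kinase, and, vitamin D levels"). The eight laboratory values are taken again at the end. No muscle, fatigue, cognitive or gastrointestinal symptom is listed at baseline, and neither is earlier statin use.

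Prior statin experience enters only through the exclusions in 5.3. A history of statin intolerance is defined in 6.1 as "History of an increase in creatine kinase OR AST/ALT elevation > 3x upper limit of normal OR rhabdomyolysis with statin initiation, prior to enrollment".

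On allocation, the Randomisation paragraph says "On the first week of enrollment, the clinician will only enroll patients into the control arm", and the intervention arm follows in the next week. Under 4.2, intervention patients at LDL goal on red yeast rice leave the analysis.

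**The concern.** Muscle aches, fatigue, mental fog and stomach upset are non-specific complaints that some patients will have before any statin. Patients enter because they decline statins (5.2), and a bad earlier experience is one plausible reason. Someone who stopped a statin because of aches, with no laboratory change, is eligible, and nothing in the record would show it. Both facts plausibly influence what a patient later blames on atorvastatin.

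Without them, the side-effect comparison gives up a covariate that could sharpen it. The trial report also could not show whether the two analysed groups began with similar symptoms. In a soundly randomised trial the second loss would be minor. Here the clinician knows the week's arm at enrolment, and one arm loses patients after allocation according to their LDL response, so comparability cannot be taken for granted.

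**Working it through.** The protocol gives no symptom rate, correlation or sample size for this endpoint, so there is no figure of its own to reproduce. All symptom inputs below are assumptions. Two sizes per arm are used: 150 (planned, section 1.1) and 69 (half of the 138 minimum in 4.5). The second serves only as a lower case, because dropout and the at-goal exclusion leave fewer than 150. The 138 itself reproduces for the primary endpoint with a one-sided 5% test: 2 × (1.645 + 1.282)² × (10/5)² ≈ 68.5, so 69 per arm.

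**1. What correlation is plausible?** Assume that a share b = 0.30 have a symptom at enrolment, that p1 = 0.50 of them later attribute it to atorvastatin, and that symptom-free patients report at rate p0. The overall rate is q = b·p1 + (1 − b)·p0, and the correlation (phi) is (p1 − p0)·√[b(1 − b)] / √[q(1 − q)], with √(0.3 × 0.7) = 0.458.
- p0 = 0.13: q = 0.241; phi = 0.37 × 0.458 / 0.428 ≈ 0.40; phi² ≈ 16%.
- p0 = 0.20: q = 0.290; phi = 0.30 × 0.458 / 0.454 ≈ 0.30; phi² ≈ 9%.
- p0 = 0.30: q = 0.360; phi = 0.20 × 0.458 / 0.480 ≈ 0.19; phi² ≈ 4%.

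**2. Precision gained by adjustment.** To a linear approximation the variance is multiplied by 1 − ρ², and N patients are worth N/(1 − ρ²) unadjusted ones.

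| ρ | Variance cut | 300 worth | 138 worth |
|---|---|---|---|
| 0.2 | 4% | 312 | 144 |
| 0.3 | 9% | 330 | 152 |
| 0.4 | 16% | 357 | 164 |
| 0.6 | 36% | 469 | 216 |

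Under the inputs of step 1 the gain is 4% to 16%. The 36% row needs a stronger link than those inputs produce.

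**3. Chance imbalance.** The SD of the difference in enrolment prevalence is √[2b(1 − b)/n]. With b = 0.30 this is √(0.42/150) = 5.3 points, or √(0.42/69) = 7.8 points. The 95% range at 150 per arm is 1.96 × 5.3 ≈ ±10 points. This variation is already in the standard error of the unadjusted comparison. It is a loss of precision, not a bias.

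**4. Systematic imbalance.** Alternating weeks or the at-goal exclusion could add to this, by an amount that the documents do not allow one to estimate. For scale, a 10-point difference in enrolment prevalence would move the endpoint by 10 × (p1 − p0): 3.7, 3.0 or 2.0 points for p0 = 0.13, 0.20 or 0.30.

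**5. Dilution when misattribution is equal in both arms.** If a share c in each arm reports an existing symptom as a drug effect, an observed rate is c + (1 − c)p. With true rates of 20% and 10%, 150 per arm and a two-sided 5% test:
- c = 0: difference 10.0 points, power 68%.
- c = 5%: 9.5 points, 55%.
- c = 10%: 9.0 points, 45%.
- c = 20%: 8.0 points, 32%.

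Baseline adjustment would recover part of this loss, to the extent shown in step 2.

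**The case against.** The strongest reply is that the endpoint is perception. A long-standing ache that the patient blames on atorvastatin is a perceived side effect, and prior expectation may be part of the mechanism under test. This stands. A reader might infer that existing symptoms are wrongly counted as drug effects; sections 3 and 4.3 and Appendix A do not support that, because the protocol does not claim to measure pharmacological effects and counts only attributed symptoms.

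A reader might also take the ±10 points in step 3 as bias. It is chance variation, and it does not inflate the type I error. The bias risk comes from the allocation method and the post-allocation exclusion. It is unquantified, and baseline questions can help reveal and adjust for an imbalance but cannot cure its cause.

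A third reply is that covariate adjustment belongs to the SAP, which is not shown. That is fair for the model, but not for the data: no SAP can adjust for a variable that was never collected, and the protocol's baseline list is itemised.

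Finally, asking about symptoms may prime reporting, and not necessarily equally. In Appendix B the control script reassures about safety, while the intervention script does not. This is a real, probably small, cost.

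**Conclusion.** The point holds as a worthwhile, inexpensive improvement to a secondary endpoint. The refill-based primary endpoint is untouched. The facts are plain in 4.2, 6.1 and Appendix A: symptoms are asked once, there is no enrolment counterpart, and subjective statin intolerance in the past is not identified.

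Two consequences are supported. The first is lost precision, worth 4% to 16% of the variance if 30% have a symptom at entry, half of them attribute it to atorvastatin, and 30% down to 13% of the others report one. It could reach 36% only at an assumed correlation of 0.6. The second is that symptom imbalance between the analysed groups can be neither described nor adjusted for, in a design where comparability is not assured.

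One further limit applies to the intervention arm. Patients who accept red yeast rice take it for two months before atorvastatin, and section 2.1 describes its active molecule as structurally identical to lovastatin. An enrolment measure alone does not give their state before atorvastatin, whereas for controls it does.

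**What to change.** - At enrolment, before either arm's script, ask the four Appendix A symptoms without attribution (for example, present in the past month: Yes, No, Not Sure). Add one item on prior statin use and the reason for stopping.
- At the existing 2-month intervention visit, repeat the four symptoms before atorvastatin is started, to describe what arose on red yeast rice. Because this answer comes after allocation, report it descriptively and do not use it as a covariate.
- Add these items to the baseline and follow-up lists in 4.2, and state that the side-effect comparison is adjusted for the enrolment items. Show those items by arm for all enrolled patients and again for those analysed.

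The cost is five questions at enrolment and four at a visit already planned. The downside is slight priming, possibly unequal between arms. The allocation method and the at-goal exclusion need their own remedy; this change does not supply it.

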4.5. Sample size/Power calculation

This study is designed as a superiority trial. Based on prior literature, we estimate a 50% statin compliance rate with a standard deviation of 10% (2). We will set the minimal detectable effect at a 5% increase in statin compliance, with an $\alpha < 0.05$ and power of 0.9. Based on case-to-control ratio of 1:1, our total minimum sample size for the primary endpoint is 138. However, we will plan on a total sample size of 300 patients, to account for patients who drop out of the study as well as patients who will be excluded due to attaining an LDL-cholesterol of <2.6 mmol/L (100 mg/dL) on red yeast rice extract.

5. Participant entry

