5.2. Inclusion criteria

1. Over 40
2. Moderate ASCVD risk
3. Decline statin therapy

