Appendix B

Clinical Encounter Conversation Guidelines

Control Group Initial Encounter

Point(s) to discuss

1. Acknowledge the patient's reluctance to start statin therapy
2. Reassure the patient that long term data supports the safety of statins
3. Reassure the patient that long term data supports the efficacy of statins

Sample Conversation(s):

"I understand that you are hesitant to start statin therapy. We over two decades of long-term follow-up data regarding statin use. The data clearly shows that statins are extremely safe and patients who stay on statins live longer and healthier lives."

Intervention Group Initial Encounter

Point(s) to discuss

1. Acknowledge the patient's reluctance to start statin therapy

2. ESC/EAS 2019 guidelines recommend an LDL-cholesterol < 2.6 mmol/L (100 mg/dL)
3. Present the option of a natural supplement as an open-ended question
4. The impact of the therapy will be assessed in two months

Sample Conversation(s):

“I understand that you are hesitant to start statin therapy. According to European guidelines, your LDL-cholesterol should be less than 2.6 mmol/L (100 mg/dL) to reduce your risk of a cardiovascular event. What is your opinion on trying a natural supplement to reduce your cholesterol?”

If the patient agrees to red yeast rice extract

“Let's follow up in two months to see if our LDL-cholesterol goals have been met”

Intervention Group Initial Follow-up

If LDL-cholesterol > 2.6 mmol/L (100 mg/dL)

Point(s) to discuss

1. Since the natural remedy did not work, we should switch to the statin to reduce cardiovascular events

Sample Conversation(s):

“Unfortunately, we were not able to meet our goals with the natural supplement. Because of this, let's try the prescription medicine instead (atorvastatin 30mg nightly)”

If LDL-cholesterol < 2.6 mmol/L (100 mg/dL)

Point(s) to discuss

1. The natural remedy did reduce your LDL-cholesterol to our original goal
2. However, the effect of the natural remedy is unreliable over time due to lack of regulation

3. Let's switch to a bio-identical prescription medicine for reliability

“Congratulations, we were able to meet our goal using a natural supplement. This supplement contains naturally occurring lovastatin; however it is difficult to predict the dose that you are receiving since supplements are not regulated. Let's try a medium dose of lovastatin instead (20mg lovastatin nightly)”

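### The allocation called block randomisation is a fixed weekly calendar rule with the arm known in advance, so the trial is quasi-randomised

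*Protocol*

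**What the plan says.** Two statements present the trial as randomised at patient level. Section 1.1 (Study summary) has "Patients will be randomized to receive either 30mg of atorvastatin or be presented with a choice", and section 4.2 (Study protocol) has "Patients will be randomized to either the control group or the intervention group".

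The Randomisation paragraph of section 4.2 names the method as block randomisation and then gives the whole procedure: "On the first week of enrollment, the clinician will only enroll patients into the control arm", and "On the subsequent week, the clinician will only enroll patients into the intervention arm". The protocol gives no random sequence, block size, random order of weeks, independent list holder or concealment step.

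Other relevant text:

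- Section 5.2 makes "Decline statin therapy" an entry criterion.
- Under section 4.2, control patients are reassured and prescribed atorvastatin at the start. In Appendix B, intervention patients are first asked "What is your opinion on trying a natural supplement to reduce your cholesterol".
- Section 4.3 makes the primary endpoint a count of pharmacy refills.
- For the sample size, section 4.5 states "we estimate a 50% statin compliance rate with a standard deviation of 10" (percent) and a minimal detectable increase of 5%.

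**The concern.** The label and the procedure contradict each other. A block design draws the order of arms at random within blocks; here the calendar sets the arm. Whoever enrols in a given week knows the arm before approaching the patient, before judging eligibility and before seeking consent.

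This trial is unusually exposed to that. Declining a statin is a soft criterion, judged in conversation. A patient who has declined is given a statin prescription in a control week and offered a supplement in an intervention week, so the patients who are approached or who agree to enter may differ by week. Willingness to take a statin plausibly drives refill counts, and it is not among the baseline variables listed in section 4.2. Adjusting for the listed variables could remove only part of an imbalance.

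What is at stake is the causal claim: a difference between arms could not be credited to autonomy with the confidence that the word randomised implies.

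**Working it through.** **1. The text.** Week one is control only and the next week is intervention only. Given the week, the arm is certain. Only two weeks are spelled out. Continued alternation is the natural reading, but the two stated weeks are already non-random.

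**2. The protocol's own sample size, as the yardstick.** Inputs from section 4.5: difference 5, SD 10, power 0.9, alpha 0.05, ratio 1:1. Per arm, n = 2(z_alpha + z_power)² × (SD/difference)².

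- One-sided: 2 × (1.645 + 1.282)² × 4 = 68.5, so 69 per arm and 138 in total. This matches the stated minimum.
- Two-sided: 2 × (1.960 + 1.282)² × 4 = 84.1, so 85 per arm and 170 in total.

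On either reading, the effect the trial must detect is 5 percentage points.

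**3. How far selection could move the comparison.** The protocol gives no figure for selection, so this is an assumed illustration. Let eligible patients be half higher compliers (mean h) and half lower compliers (mean l), averaging 50%.

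- Control mean if a share q of the lower group does not enter in control weeks: (0.5h + 0.5(1 − q)l) / (0.5 + 0.5(1 − q)).
- Intervention mean if that share enters in intervention weeks instead: (0.5h + 0.5(1 + q)l) / (0.5 + 0.5(1 + q)).

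The between-group SD is (h − l)/2. A 60/40 mix has SD 10, the widest equal mix that fits section 4.5. An 80/20 mix has SD 30, three times the protocol's value.

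| Mix | q | Control mean | Intervention mean if deferred | Difference |
|---|---|---|---|---|
| 60/40 | 0.2 | 46/0.9 = 51.1 | 54/1.1 = 49.1 | -2.0 |
| 60/40 | 0.3 | 44/0.85 = 51.8 | not computed | not computed |
| 80/20 | 0.2 | 48/0.9 = 53.3 | 52/1.1 = 47.3 | -6.1 |
| 80/20 | 0.3 | 47/0.85 = 55.3 | not computed | not computed |

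So non-entry alone raises control compliance by 1.1 to 1.8 points (60/40) or 3.3 to 5.3 points (80/20). Deferral in the opposite direction reverses the sign: +2.0 to +6.1.

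**4. Secondary: assignment by week also creates clusters.** Inputs: 300 patients and four centres (section 4.2), six months taken as 26 weeks, and an assumed ICC of 0.01 to 0.05. Design effect = 1 + (m − 1) × ICC.

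- Centre-weeks: m = 300/(4 × 26) = 2.88. Design effect 1.02 to 1.09; 138 becomes about 141 to 151.
- Calendar weeks shared by all centres: m = 300/26 = 11.54. Design effect 1.11 to 1.53; 138 becomes about 153 to 211.

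**The case against.** The contradiction itself has no good answer. The objections concern what is built on it.

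- **The bias figures are assumed.** This stands. With the protocol's SD, the illustrated shifts are 2.0 points or less, under half the target. Those that reach 5 points need an SD of at least 30. All eligible patients have declined statins, which may narrow the spread in willingness further.
- **The likeliest mechanism works against the hypothesis.** Reluctant patients staying out of control weeks raises control compliance and so masks a benefit. The documents give no particular reason for the opposite direction. This is fair, but a masked effect is also a wrong answer, and nothing in the rule prevents selection the other way.
- **Patient self-selection is not shown.** Section 9.2 does not say who seeks consent or whether the arm is disclosed first. Only the clinician's foreknowledge follows from the text. That is enough to defeat concealment.
- **Clustering is minor.** This is true. The ICC is assumed, the analysis could be handled in a SAP, and even 211 is below the planned 300. The figures also hold accrual at about 11.5 patients a week. If cluster size shrinks with the total, solving N = 138[1 + (N/26 − 1) × ICC] gives only about 144 to 179. The case rests on bias, not power.

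**Conclusion.** The concern holds. The protocol describes deterministic allocation by calendar week and calls it randomised. As written, the trial is quasi-randomised, and the enrolling clinician knows the arm before eligibility is judged. This follows from the text and needs no assumption beyond alternation continuing past the second week.

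The size and sign of the resulting bias are unknown. With 20% deferral the illustration gives 2.0 points in either direction with a mix that fits the protocol's SD, and 6.1 points with a far wider one, against a target of 5. These figures show that modest selection can matter; they do not estimate it. The rule must be changed before enrolment, because neither a larger sample nor a later analysis plan can supply the missing randomisation.

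**What to change.** Replace the Randomisation paragraph with wording such as: *Patients will be individually randomised 1:1 from a computer-generated permuted-block list with varying block sizes, stratified by centre. The allocation is released through the online CRF only after eligibility, consent and baseline data have been entered.*

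Section 6.2 already plans the platform ("An online CRF form will be used throughout the study") but mentions no randomisation function, so one would have to be added. Section 9.7 says the study is unfunded. If the CRF cannot do this, sequentially numbered, opaque, sealed envelopes prepared by someone outside enrolment are the cheap fallback at four centres.

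The cost is one paragraph plus that function or the envelopes. The drawback is that clinicians would deliver both scripts within the same week. They already deliver both in successive weeks under the present rule, so the added contamination risk is probably small, though the documents give no data on it.

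If weekly assignment must stay, randomise the order of weeks within each centre, obtain consent before the week's arm is revealed, account for week clusters in the analysis, and do not describe the trial as randomised at patient level. This is clearly weaker: once the first patient of a week is allocated, the same clinician knows the arm for the rest of that week. Keeping the present rule and relabelling the trial quasi-randomised would remove the contradiction but not the bias.
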